	
The end-tidal anesthetic gas concentration will be time-locked to the BIS™ system recordings. End-tidal sevoflurane, oxygen, and nitrous oxide concentrations will be downloaded from the anesthetic monitoring device, and de-identified digital copies will be provided to Medtronic.
 
Time and values of BIS™, ET_{SEVO} concentration (%) and other medication, FiO₂(%) and EtO₂(%), EtCO₂(%) will be recorded at the following time intervals:
 
• Baseline• Study start• At IV placement, as applicable• Start of induction• Start of N₂O, as applicable• Start of sevoflurane• Anesthesia Airway Management (AAM)• AAM change (including type of AAM)• At any airway reflex (coughing, choking, layngospasm)• Every 15 min after airway management• At all medication administration (as applicable)• N₂O off (as applicable)• Start of the surgery/procedure• Skin incision, if applicable• End of surgery/procedure (or skin dressing or cast or splint applied or abdominal block)• Skin closure, if applicable• Sevoflurane off• Termination of all anesthesia• Extubation• Physician Awakening subject, if applicable• Time of emergence (if occurs in OR)• End of study (removal of device)
--	---

	
• 15 min post dexmedetomidine administration, if applicable• Time moved to PACU 
Recovery Assessments
 
Subject recovery will be observed continuously after the termination of anesthesia for presence of coughing, choking, laryngospasms, and emergence. Emergence is defined as the time when any of the following first occurred:
 
• eyes open spontaneously,• crying or phonating, or• purposeful movements. 
The time of emergence, time subject moved to PACU, and time of readiness for discharge will be recorded. The time of these assessments will be captured in medical records, source, and recorded on the eCRFs.
 
All subjects will be assessed at 15-minute intervals beginning at anesthesia termination:
 
• Vitals Signs• Pediatric Anesthesia Emergence Delirium (PAED)• Wong-Baker FACES Pain Scale (when subject is awake)• PACU discharge readiness - Modified Aldrete Score

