10.9.6 Recovery

Subject recovery will be continuously after the termination of anesthesia for presence of coughing, choking, laryngospasms, and emergence.

Emergence is defined as the time when any of the following first occurred:

- eyes open spontaneously,
- crying or phonating, or
- purposeful movements.

The time of emergence, time subject moved to PACU, and time of readiness for discharge will be recorded. The time of these assessments will be captured in medical records, source, and recorded on the eCRFs.

All subjects will be assessed at 15-minute intervals:

- Pediatric Anesthesia Emergence Delirium (PAED)
- Wong-Baker FACES Pain Scale (when subject is awake)
- PACU discharge readiness - Modified Aldrete Score

PAED, Wong-Baker FACES Pain Scale, and Modified Aldrete Score data will be recorded in source every 15 minutes. Raw data but total scores for the highest amount of delirium from the PAED, the highest amount of pain from the Wong-Baker FACES Pain Scale and the least ready for discharge Modified Aldrete Score raw data will be entered in to the CRF. The final raw data and total scores for the PAED, Wong-Baker FACES Pain Scale and Modified Aldrete Scale will be entered into the eCRF.

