10.9.6.4 Modified Aldrete Score

End of surgery to post-anesthesia care unit (PACU) discharge readiness will be assessed using the Modified Aldrete Score that examines the following five criteria: motor activity, respiration, blood pressure, consciousness, and color [15, 16]. Before a subject can be safely discharged from the PACU, a score of 12 out of 16 points based on the PACU standard discharge criteria will be achieved. The time and score of PACU discharge readiness will be recorded. The scale is included in **Appendix C**.

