14.1 General Aspects of Analysis

Standard demographic information and baseline characteristics will be summarized using descriptive statistics. For safety assessments, adverse events (AEs) will be summarized using frequency counts and percentages. Descriptive statistics will be provided by severity and relationship as needed.

The primary endpoint will be collected as a continuous variable every minute along with the BIS values. The primary analysis will be based on all evaluable data (excluding training subjects). Normality of data will be tested using the Kolmogorov-Smirnov test. Depending on whether normality assumption holds, a two-group t-test or Wilcoxon rank-sum test will be used to compare between the two treatment groups. A *P*-value of less than 0.05 is considered statistically significant unless otherwise specified.

The training subjects will not be included in the analysis set for the primary and secondary endpoints. The training subjects will be summarized descriptively and separately. Any specific findings from these subjects will be noted and discussed in the study report.

The following secondary endpoints will be evaluated:

- Time to first response (emergence)
- Time to PACU discharge readiness using Modified Aldrete Score
- Time to extubation

Upon meeting the primary endpoint, the secondary endpoints will be evaluated using the Holm-Bonferroni method. The method is a sequentially rejective multiple test procedure used to adjust multiplicity and to ensure the overall type I error rate is controlled at the 0.05 level. For statistical inferences, categorical variables will be evaluated using the Chi-square test or Fisher's exact test, and continuous variables will be evaluated using the t-test or Wilcoxon rank-sum test as appropriate. The analysis details will be clearly specified in the Statistical Analysis Plan.

Data Poolability

The clinical study will be conducted under a common protocol for each investigational site with the intention of pooling the data for analysis. Every effort will be made to promote consistency in study execution at each study site.

An assessment of data poolability of the sites will be performed using a mixed-effect model for the primary endpoint. A significance level of 0.15 will be considered. Sites with fewer than five subjects will be combined into large sites to ensure statistical robustness.

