7.9 Evaluation of Objectives

Standard demographic information and baseline characteristics will be summarized using descriptive statistics. For safety assessments, adverse events (AEs) will be summarized using frequency counts and percentages. Descriptive statistics will be provided by severity and relationship as needed.

The primary endpoint will be collected as a continuous variable every minute along with the BIS™ values. The primary analysis will be based on all evaluable data (excluding training subjects). Normality of data will be tested using the Kolmogorov-Smirnov test. Depending on whether normality assumption holds, a two-group t-test or Wilcoxon rank-sum test will be used to compare between the two

treatment groups. A P-value of less than 0.05 is considered statistically significant unless otherwise specified.

The mean BIS™ and standard deviation will be determined at each concentration of sevoflurane. A semi-logarithmic plot of sevoflurane concentration versus BIS™ will be provided, and the correlation will be quantified by using an inhibitory sigmoid E_{max} model (Denman et al., 2000) on steady state points. The model is formulated as:

$$E = E_0 - \frac{(E_{max})(C^\gamma)}{EC_{50}^\gamma + C^\gamma}$$

As noted by Denman, the E_0 is specified to be 100, γ (gamma) is the scale factor, and E_{max} is the maximal effect constrained to 100. The EC_{50} is the sevoflurane concentration corresponding to the half-maximal effect (e.g., BIS™ of 50), and this value will be estimated, along with 95% confidence intervals, for each age group.

The training subjects will not be included in the analysis set for the primary and secondary endpoints. The training subjects will be summarized descriptively and separately. Any specific findings from these subjects will be noted and discussed in the study report.

The following secondary endpoints will be evaluated:

- Time to first response (emergence)
- Time to PACU discharge readiness using Modified Aldrete Score
- Time to extubation.

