Upon meeting the primary endpoint, the secondary endpoints will be evaluated using the Holm-Bonferroni method. The method is a sequentially rejective multiple test procedure used to adjust multiplicity and to ensure the overall type I error rate is controlled at the 0.05 level. For statistical inferences, categorical variables will be evaluated using the Chi-square test or Fisher's exact test, and continuous variables will be evaluated using the t-test or Wilcoxon rank-sum test as appropriate.

Cardiovascular variables will be summarized for both treatment groups. The incidence of hypotension will be summarized and compared to anesthesia sedation levels.

The anesthetic requirements with the BIS™ value, the percentage of time during maintenance with BIS™ value within the specified ranges, and number of episodes and duration of burst suppression will be assessed for the BIS and SP groups.

Additional endpoints, including the PAED scale, PACU discharge readiness, Anesthesia Airway Management, and a subgroup analysis for subjects requiring neuromuscular blockade, will be evaluated by using descriptive statistics and compared between BIS and SP groups.

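### Time to PACU discharge readiness rests on a score taken every 15 minutes but is analysed as an exact time; the plan should say which time counts and summarise it as interval-censored

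*Protocol*

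**What the plan says.** **Schedule.** The synopsis (Recovery Assessments) states: "All subjects will be assessed at 15-minute intervals beginning at anesthesia termination". Protocol 10.9.6 repeats the interval without the starting point ("All subjects will be assessed at 15-minute intervals") and adds that "Modified Aldrete Score data will be recorded in source every 15 minutes". Only coughing, choking, laryngospasm and emergence are to be watched continuously. The version history shows that version 3.0 widened the recovery checks from 5 to 15 minutes. The SAP introduction says that it elaborates CIP 2.0.

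**Readiness time.** Protocol 10.9.6 says: "The time of emergence, time subject moved to PACU, and time of readiness for discharge will be recorded". Section 10.9.6.4 links time and score: "The time and score of PACU discharge readiness will be recorded". Table 5 in section 10.2 gives the score and the readiness time separate rows. From the serial Aldrete scores, the eCRF is to hold the least-ready and the final one.

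**Analysis.** Protocol 14.1 and SAP 7.9 list "Time to PACU discharge readiness using Modified Aldrete Score" among three secondary endpoints. Protocol 14.1 says "Upon meeting the primary endpoint, the secondary endpoints will be evaluated using the Holm-Bonferroni method", and SAP 7.9 says that "continuous variables will be evaluated using the t-test or Wilcoxon rank-sum test as appropriate". No method for interval-censored times is named.

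**The concern.** Readiness is reached when a score crosses a threshold, and that score is scheduled only at 15-minute checks. The natural reading is that the recorded time is the first check at which the threshold is met. A child ready at 16 minutes and one ready at 29 would then both be recorded at 30, and one ready at 14 at 15. The protocol's own background study found a readiness difference of 6.7 minutes, less than half of the interval.

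At stake is how the endpoint is reported. Arm means would be too long, and the medians that SAP 7.2 lists for continuous variables could be identical when the true ones differ by about 6 minutes. If some sites time readiness between checks and others do not, precision would also differ by site.

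**Working it through.** **The plan's own figure.** Protocol 14.2 states power only for the primary endpoint: more than 80% for a 0.5% difference, SD 0.5%, 18 per arm. Check: 0.5 / (0.5 × √(2/18)) = 3.00, and 3.00 − 1.96 = 1.04, which gives 85.1% (83.0% with the t distribution). It reproduces. There is no stated power for readiness to reproduce.

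**Inputs for readiness**
- SP 26.7 (SD 11.2) and BIS 20.0 (SD 7.9) minutes, ages 3–18: protocol 4.1.3.2, Table 3. Difference 6.7.
- 54 per arm (3 × 18): protocol 14.2.
- First Holm step: 0.05/3 = 0.0167.
- Assumption: recorded time = true time rounded up to the next 15-minute check.
- Assumption: the background figures are exact times. The documents do not say how often that study assessed readiness.

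**Shift.** Rounding up to a grid of width g adds about g/2 on average: 15/2 = 7.5 minutes. With gamma-distributed times, the simulated recorded means are 34.2 and about 27.4, so the difference remains about 6.7. Across gamma, lognormal and normal times, the overstatement is 7.4–7.6 minutes per arm and the difference 6.7–6.9. On a 5-minute grid the overstatement is 2.5 minutes.

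**Medians, clock and checks starting together.** With gamma times, the shares recorded at 15, 30 and 45 minutes are:

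| Arm | 15 | 30 | 45 |
|---|---|---|---|
| SP | 13.4% | 53.0% | 26.9% |
| BIS | 28.8% | 60.2% | 10.4% |

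The true medians are 25.1 and 19.0; both recorded medians are 30. The SP sample median leaves 30 upward only if at least 27 of 54 children exceed 30 minutes, each with probability 1 − 0.134 − 0.530 = 0.336. That happens in about 1% of trials, so both medians read 30 in about 99%. With normal times the probability is 1 − 0.148 − 0.468 = 0.384, and both medians read 30 in about 95%.

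**Power**
- Pooled SD, exact times: √((11.2² + 7.9²)/2) = 9.69.
- Pooled SD, 15-minute grid: √(9.69² + 15²/12) = 10.61.
- Standard errors with √(2/54): 1.865 and 2.043. Ratios to 6.7: 3.59 and 3.28.
- At 0.0167 (critical value 2.394): 88.5% and 81.2%. At 0.05: 94.9% and 90.7%.

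Gamma simulation at 0.0167: t-test about 88% to 80%, rank-sum about 83% to 76%. A 5-minute grid costs almost nothing (t-test about 88%).

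**What an interval-censored analysis returns.** Lognormal interval-censored fits to the 15-minute data gave means of 26.5–26.8 and 19.9–20.0, with power of 79–80%. The arm times come back; the power does not.

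**The case against.** The strongest reply is that rounding up is inferred. The synopsis, Table 5, 10.9.6 and 10.9.6.4 all treat readiness time as its own data item, and none confines it to a check. This stands, so every figure above is conditional. It does not remove the point: 10.9.6.4 pairs the time with a score that is scheduled only every 15 minutes, and no text allows a reading in between.

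Other replies also have force:
- **The comparison is not biased.** Both arms shift by the same amount. The shift does reduce the relative reduction (6.7/26.7 = 25% becomes 6.7/34.2 = 20%), but neither document plans to report that quantity.
- **The interval can be approximated.** If checks run exactly on schedule, readiness lies in the 15 minutes before the recorded time, and every check is in source. It would be too strong to say that the interval cannot be rebuilt. The extra eCRF time matters when checks run off schedule.
- **The median result needs a common origin.** The synopsis starts checks at anesthesia termination, 10.9.6 gives no start, and 10.9.6.4 counts from end of surgery. With different origins, times need not pile up on 15, 30 and 45; the mean overstatement of about 7.5 minutes remains.
- **The inputs are borrowed.** They come from tonsillectomy and adenoidectomy under nitrous oxide, and are not a planning assumption of this trial.
- **A simple correction exists.** Subtracting 7.5 minutes roughly restores the means. It does not restore the medians or handle off-schedule checks.

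**Conclusion.** The point holds as a conditional one and is worth a cheap correction. The plan does not say which time defines readiness. If it is the first passing check, treating it as exact lengthens each arm's reported mean by about 7.5 minutes. With aligned clocks and the background figures, it also hides a real difference in medians.

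A reader might infer that the treatment comparison is biased or the test invalid. The documents do not support that: the schedule is the same in both arms, and the mean difference stays near 6.7 minutes. A reader might also infer a serious loss of power. The loss is about 7 to 8 points at the first Holm step with 54 per arm, for an endpoint that was never formally powered. Nor do the documents establish that recorded times will in fact be rounded up.

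Two contradictions bear on the endpoint and must be reconciled:
- Protocol 10.9.6.4 requires 12 of 16 points, while the five-item scale in Appendix C totals at most 5 × 2 = 10.
- Protocol 14.1 and SAP 7.9 test the secondary endpoints under Holm, SAP 7.5 rules out any multiplicity adjustment, and both 14.1 and 7.9 also list discharge readiness among endpoints handled with descriptive statistics.

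**What to change.** 1. Keep the 15-minute schedule. In protocol 10.9.6 and 10.9.6.4, state which time defines readiness, whether it may fall between checks, and the origin from which it is counted.
2. Enter two times in the eCRF from source: the last check not meeting the readiness criterion and the first check meeting it.
3. In SAP 7.9, report arm medians or means and the treatment contrast from an interval-censored analysis, for example a parametric accelerated-failure model, with a generalised log-rank test as an alternative for the comparison. Keep the t-test or rank-sum as a supporting analysis.
4. Reconcile the readiness threshold in 10.9.6.4 with the Appendix C scale, and SAP 7.5 and the descriptive listings with the Holm procedure.

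The cost is one extra eCRF time that already exists in source, some SAP wording and a slightly more complex analysis. The gain is correct reported times; the lost power is not recovered.

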10.9.6.1 Presence of laryngospasms, coughing, choking

Presence of laryngospasms, coughing, choking as indicated by the anesthetist, if any present, time, and treatment course will be documented.

10.9.6.2 Pediatric Anesthesia Emergence Delirium (PAED)

Both groups will be assessed using the Pediatric Anesthesia Emergence Delirium (PAED) scale [1]. The PAED is an observational scale that has been validated in children to detect and measure the severity of hyperactive emergence delirium upon awakening from anesthesia. The scale includes 5 items: 1) Child makes eye contact with the caregiver, 2) child's actions are purposeful, 3) child is aware of his/her surroundings, 4) child is restless, 5) child is inconsolable. The scale is included in **Appendix A**. The time and treatments/conmedications given for delirium and will be documented.

10.9.6.3 Wong-Baker FACES Scale

The Wong Baker FACES pain scale is an instrument validated for ages 3+ to measure pain, by selecting a number on an ordinal 0-10 scale (“0” being no pain and “10” being the worst pain ever). Subjects will be instructed to indicate their degree of pain prior to being discharged from the PACU. The Wong-Baker FACES Scale will be administered when the subject is awake and able to perform the assessment. For more information, refer to **Appendix B**.

10.9.6.4 Modified Aldrete Score

End of surgery to post-anesthesia care unit (PACU) discharge readiness will be assessed using the Modified Aldrete Score that examines the following five criteria: motor activity, respiration, blood pressure, consciousness, and color [15, 16]. Before a subject can be safely discharged from the PACU, a score of 12 out of 16 points based on the PACU standard discharge criteria will be achieved. The time and score of PACU discharge readiness will be recorded. The scale is included in **Appendix C**.

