In the BIS™ group, fentanyl and morphine administration will be at the discretion of the anesthesiologist, for example, fentanyl and morphine 1.5 mcg/kg at induction and 0.75 mcg/kg every 30 minutes, using clinical signs and cardiovascular changes, however sevoflurane will be adjusted to achieve a target BIS™ values of 45 – 60 during maintenance of anesthesia and BIS™ values of 60 – 75 beginning of skin closure. Subjects with BIS™ values that are outside of the specified range of 45 – 60 during maintenance of anesthesia for >35% of the maintenance duration will be considered a protocol deviation and the subject will be excluded from the final data analysis and will be replaced by an additional subject. The excluded subject will continue to be monitored for any safety events and the clinical will ensure that medical care is provided should a safety event occur. Data from the excluded subject will be acknowledged in the final study report but will not be included in the primary statistical analysis. The exception to this exclusion is any data that is outside of the specified range of 45 – 60 as a result of the anesthesiologist titrating medications as a result of clinical signs or cardiovascular changes defined above. Additionally, data points will be excluded if significant artifact is present or if the sevoflurane concentration or BIS™ value is missing.

At the completion of the surgery, and after confirmation of the return of neuromuscular function, sevoflurane will be discontinued, and discontinuation time will be recorded, and as applicable, extubation will be performed when the patients demonstrate the purposeful movement, facial grimace, or eye-opening to jaw thrust.

Event Markers and Assessments

During the case, the time of events (for example start of induction, LOC, airway management /intubation (as applicable), the start of the procedure, incision, N₂O off (as applicable), sevoflurane off, extubation (as applicable), eye-opening, end of the procedure, move to PACU, and PACU discharge readiness) will be recorded.

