10.2 Data Collection

Table 5: Data collection and study procedure requirements at subject visits

Study Tasks	Baseline/ Enrollment	Surgical Procedure			PACU/ Discharge
		Randomization	Induction and maintenance	End of Surgery	
Baseline					

Medtronic Business Restricted

Study Tasks	Baseline/ Enrollment	Surgical Procedure			PACU/ Discharge
		Randomization	Induction and maintenance	End of Surgery	
Informed Consent ¹	x				
Inclusion/exclusion criteria review and confirmation of eligibility status	x	x			
Demographics ²	x				
Medical History ³	x				
Pre-operative Vital Signs ³	x				
Procedure					
Randomization (before the procedure for group assignment) ⁴		x			
BIS™ and Nellcor™ sensors placement			x	x	
BIS™, Nellcor™ and other digital data collection			x	x	
Standard surgical procedures			x	x	
ET _{SEVO} concentration and other drug information			x	x	
Cardiovascular Variables ⁵	x		x	x	
Event Markers and Assessments collection ⁶			x	x	
Anesthesia Airway Management ⁶			x	x	
Recovery					
Emergence ⁷				x	x
Incidents of postop nausea and vomiting ⁷				x	x
Vitals ⁷				x	x
Wong-Baker FACES Scale ⁷				x	x
Pediatric Anesthesia Emergence Delirium (PAED) ⁷				x	x
Modified Aldrete Score				x	x

Study Tasks	Baseline/ Enrollment	Surgical Procedure			PACU/ Discharge
		Randomization	Induction and maintenance	End of Surgery	
Time of Readiness for PACU discharge ^{6,7}				X	X
Exit					
Reason for Study Exit ⁸	X	X	X	X	X
Safety					
Adverse Event Assessment ⁹	X		X	X	X
Device Deficiency ⁹			X	X	

- 1) Written informed consent must be obtained before any study-specific evaluations, *Section 10.5*
- 2) Demographic information, including sex, weight, height, age, ethnicity, race, as well as skin tone, will be recorded refer to *Section 10.6*.
- 3) Relevant Medical History, including diagnosis and surgery type, will be collected, *Section 10.7*
- 4) Randomization will be performed before the surgical procedure for group assignment refer to *Section 10.8*.
- 5) Cardiovascular Variables (heart rate [HR]; systolic and diastolic blood pressure [BP] including hypotension; oxygen saturation; and temperature) refer to *Section 10.9*.
- 6) For event markers and assessments, refer to *Section 10.9*
- 7) For recovery data collection, refer to *Sections 10.9*.
- 8) Details are included in *Section 10.14..1*
- 9) Details are included in *Section 12*.

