10.8 Randomization and Treatment Assignment

Prior to Randomization, 2 - 4 subjects from each site will be consented and enrolled. The data will be used to train on the new technology use, and to review the quality of the data collection, refer to *Section 10.2*.

Subjects are eligible for randomization assignment after study enrollment and verification of eligibility criteria. Subjects will be randomized in a 1:1 fashion to the BIS™ group or standard practice group using the RDC electronic system. Randomization schedules will be created by a Medtronic statistician, and randomization assignments will be automatically populated on the Randomization e-CRF after subject consent and eligibility verification have been entered in RDC. The randomization schedule will be stratified by age group and the study site to ensure 1:1 randomization within each study site.

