Appendix C – Modified Aldrete Scoring System [15, 16]

ACTIVITY	Able to move all extremities voluntarily on command	2
	Able to move 2 extremities voluntarily on command, some weakness	1
	Unable to move extremities	0
RESPIRATION	Able to deep breathe and cough without assistance	2
	Requires airway assistance	1
	Apnea	0
CIRCULATION	Blood pressure and heart rate are within 20% of presedation level	2
	Blood pressure and heart rate are within 20-50% of presedation level	1
	Blood pressure and heart rate are less than 50% of presedation level	0
CONSCIOUSNESS	Fully awake, able to answer questions as appropriate	2
	Arousable with verbal stimulation	1
	Unresponsive	0
OXYGENATION	Able to maintain oxygen saturation >92 percent on room air	2
	Requires supplemental oxygen to maintain oxygen saturation >92 percent	1
	Oxygen saturation <92 percent even with supplemental oxygen	0

19. Version History

Version	Summary of changes	Author(s)/Title
1.0	
Not Applicable, New Document	[name]./ Sr. Clinical Program Manager [name]/Sr. Clinical Research Specialist
2.0	
Revision to new Operating UnitCorrection to Wong-Baker Collection criteria	[name], Sr. Clinical Research Specialist
3.0	
Changes to title page to remove unused rowsAddition of signal quality index (SQI) to glossaryChange definition of time of surgical procedure to maintenance duration to align with statistical analysis planIncrease number of sites up to eightAddition of pre-operative vitals obtained in pre-operative holding to baseline/enrollment visit procedures and assessmentsChange of surgeries approved for study to allow for approval of additional surgery types by study teamChange in allowed % of time outside of BIS range for BIS-guided subjects from 25% of 35% to improve number of qualifying cases (business decision)Change in Wong-Baker FACES Pain Rating Scale to be performed only when subject is awake to avoid unnecessary protocol deviationsCompletion of recovery assessments changes from every 5 minutes to every 15 minutesAddition of required variables to list of timepoints for BIS, ETSevo, FiO2, and EtO2 data collection needed for outcome analysisClarification of procedure and recovery variables	[name]., Sr. Clinical Research Specialist

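### The PACU discharge threshold of 12 out of 16 cannot be reached on the Modified Aldrete scale in Appendix C, which has a maximum of 10

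*Protocol*

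**What the plan says.** Protocol 10.9.6.4 makes the Modified Aldrete Score the instrument for readiness to leave the PACU, timed from the end of surgery. It gives five criteria: "motor activity, respiration, blood pressure, consciousness, and color". It then requires that "a score of 12 out of 16 points based on the PACU standard discharge criteria will be achieved" before a subject leaves, adds that "The time and score of PACU discharge readiness will be recorded", and points to Appendix C for the scale.

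Appendix C sets out activity, respiration, circulation, consciousness and oxygenation, each with levels 2, 1 and 0. The top level of the fifth item, for example, is "Able to maintain oxygen saturation >92 percent on room air".

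The readiness time is also collected as an event in its own right:

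- Synopsis, Event Markers and Assessments: "end of the procedure, move to PACU, and PACU discharge readiness) will be recorded".
- Table 5 in Protocol 10.2 has a row for "Time of Readiness for PACU discharge".
- Protocol 10.9.6: "time subject moved to PACU, and time of readiness for discharge will be recorded".

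Protocol 10.9.6 also has the score taken every 15 minutes and kept in source, with the least-ready and final scores entered in the eCRF.

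Protocol 14.1 and SAP 7.9 list time to readiness by this score among three secondary endpoints, to be evaluated by Holm-Bonferroni if the primary endpoint is met. Neither section states a threshold.

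**The concern.** A time-to-readiness endpoint needs a definition of readiness. The only numerical definition in either document exceeds the maximum of the scale it is attached to. Staff who follow the protocol literally would never see a subject qualify, so in practice they must use some other cut-off. With up to eight sites (Protocol 9.1), that cut-off could differ from one site to another, and the recorded readiness times would then not all measure the same thing. The rule is also worded as a condition for safe discharge, which is a further reason for it to be usable.

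**Working it through.** **Inputs**

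- Stated threshold and maximum: 12 and 16 (Protocol 10.9.6.4).
- Number of criteria: 5 (Protocol 10.9.6.4 text; Appendix C also shows 5).
- Points per item: 0, 1 or 2 (Appendix C, all five items).

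**Step 1: try to reproduce the stated maximum.** Sum of item maxima = 2 + 2 + 2 + 2 + 2 = 5 × 2 = 10. The stated 16 is not reproduced.

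**Step 2: compare the threshold with the attainable range.** Totals run from 0 to 10, and 12 − 10 = 2, so the threshold lies 2 points above the maximum. Listing all 3^5 = 243 combinations of item scores confirms this: 0 of 243 reach 12.

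**Step 3: could items have been lost in the appendix?** A total of 16 in this format needs 16 / 2 = 8 items. The section text independently says five criteria, and all five appendix items are complete with three levels each. Nothing points to three missing items.

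**Step 4: can the intended cut-off be recovered by rescaling?** 12 / 16 = 0.75, and 0.75 × 10 = 7.5, which is not a possible score. Rounding down or up gives rules of different strictness. As a count of score patterns only (not a probability for patients), the numbers of the 243 combinations that qualify are:

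| Cut-off | Combinations that qualify |
|---|---|
| ≥ 7 | 51 |
| ≥ 8 | 21 |
| ≥ 9 | 6 |
| 10 | 1 |

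The documents give no basis for choosing among these.

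**Step 5: compare the item lists.** Section 10.9.6.4 lists blood pressure and color. Appendix C scores circulation (blood pressure and heart rate) and oxygenation. This does not change the maximum, but it is a second mismatch between the section and the scale it cites.

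**Step 6: look for a correction elsewhere.** Protocol 14.1 and SAP 7.9 name the endpoint without a threshold. No other cut-off and no 16-point instrument appears in either document.

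**The case against.** The strongest counter-reading is that the threshold sentence refers to standard PACU discharge criteria. These might be a separate 16-point checklist used in routine care, on which 12 is attainable. This cannot be excluded, but it is the weaker reading. The sentence sits between the description of the five-criterion score and the pointer to Appendix C, and no such checklist is named or appended. If it is nevertheless right, the protocol still lacks a readiness cut-off on the score that defines the endpoint.

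It is also fair to say that site training or the case report form completion guidelines, which are not among the documents, may supply a common working cut-off. Variation between sites is therefore a possibility and has not been shown.

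Several facts limit the consequence, and they stand:

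- Readiness time is recorded directly, and scores are kept in source every 15 minutes, so data exist to which a corrected rule could be applied.
- Under Protocol 10.8, "The randomization schedule will be stratified by age group and the study site to ensure 1:1 randomization within each study site". A cut-off peculiar to a site would therefore be expected to affect both arms there.
- The endpoint is tested only if the primary endpoint is met.
- Protocol 14.1 and SAP 7.9 also list PACU discharge readiness among additional endpoints to be described and compared.

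These points bear on how serious the error is. They do not remove it.

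**Conclusion.** The concern holds. As written, the threshold is 2 points above the maximum of the cited scale, and neither document supplies a usable alternative. This is an incorrect decision rule behind a formally tested secondary endpoint and should be fixed. The conclusion rests on reading the threshold as applying to the Appendix C scale, which the order of the section supports. On the other reading, the defect becomes an unidentified instrument, and a correction is still needed.

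No directional bias between arms is shown. A different cut-off could move the qualifying 15-minute assessment by one or more intervals, but how often that would happen cannot be derived from the documents, so no size of loss is claimed. The primary endpoint and the sample size are unaffected.

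**What to change.** 1. Correct Protocol 10.9.6.4 so that its items, maximum and threshold agree with Appendix C. Use one attainable cut-off of 10 or less, chosen by the sponsor's clinical advisers and applied at every site. If a 16-point tool was intended, name it, append it and say how it relates to the endpoint.
2. Carry the threshold, and the end-of-surgery time origin already in 10.9.6.4, into the SAP and the eCRF.
3. If enrolment is under way, choose the cut-off blind to treatment arm and before database lock.
4. Keep the directly recorded readiness time as the event time, and use the source scores to check that the cut-off was met. The source scores come only every 15 minutes and the eCRF holds only the least-ready and final ones, so they are a coarser basis for the event time. A sensitivity analysis taking the first source score at or above the cut-off would be a useful addition for subjects already treated.

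The cost is a text and eCRF correction, a training note to sites and possibly some source checks for subjects already treated. No extra assessments or patients are needed.
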